This project aims to demonstrate that emergent, non-invasive, non-anesthetic laser therapy has significant benefit for BCS with AI, measured in a prospective, randomized, double-blind controlled trial using validated tools for subjective and objective sexual and vaginal health outcomes and quality of life.

Moreover, sexual health is a state of physical, emotional, mental and social well-being in relation to sexuality which requires the possibility of having pleasurable and safe sexual experiences [1]. So, both arms of study groups will benefit from multidisciplinary approach including non-hormonal therapies (regular sexual activity, moisturizers, lubricants, pelvic floor relaxation techniques and/or dilators) and sexual assessment using the PLISSIT Model according with usual care in our hospital and with international recommendations [7, 8, 18].

ETHICAL AND REGULATORY PERMISSIONS:

Please explain the ethical and regulatory permissions already obtained or to be obtained for (if applicable):

- 1) *Animal research*
- 2) *Human tissue*
- 3) *Research with human participants*

If the permissions have not been obtained already, please give timelines of when they are expected to be obtained and how obtaining such permissions will affect the overall project timelines.

This study will be conducted according to the Helsinki Declaration and to Good Practice Guidelines. Approval from Ethics Committee of Hospital Clínic de Barcelona has been recently applied (August 2020) and the study will be registered on ClinicalTrials.gov. As we are on holiday time in Spain (August) and also due to the current COVID-19 situation in Barcelona, a delay in the usual approval rhythm of our ethical committee is expected. However, we hope to obtained such a permission on October 2020, which will not affect the overall project timelines.

All eligible women will be informed about the study by briefing the participants on the study objectives and taking into account their willingness to participate (telematic visit). After an interval of at least 48h the patient will have a second visit (presential) and if she wants to participate the signed informed consent form will be checked. Both in- and exclusion criteria will be reviewed and if found suitable, the patient will be randomized. Both the patient information letter and informed consent form are attached as a separate document. Patients can leave the study at any time for any reason if they wish to do so without any consequences. The investigator can decide to withdraw a subject from

the study for urgent medical reasons. Patients who withdrew their informed consent will not be replaced. We will replace patients that are randomized by mistake, for example because of technical errors with online randomization. Patients withdrawn from the intervention but not from informed consent will be followed up.

None of the subjects will receive any (financial) compensation for participating in this trial. However, to minimize dropouts and build patient loyalty, we will offer them at the end of the study an additional laser treatment session, and those in the placebo group will be offered the 5 treatment sessions.

BUDGET:

Please give a detailed and itemized budget, see T&C for eligible and ineligible costs

Execution Expenses

A) Personnel costs

A postgraduate research student ([name]) will be hired 15h/week during 18months in order to perform task described in the Workplan. In addition, will be in charge of:

- Transcription of data to database.
- Management and coordination of patient appointments, as well as evaluation and resolution of problems derived from the study.
- Evaluation of results.
- Writing of manuscript.

B) Acquisition of materials and contracting of services

PH meter paper roll 5m x 2 IU x 10 = € 20

Maturation index (provided by Hospital Clinic de Barcelona): 12€ x 264 (88 patients throughout the study in 3 timepoints) = 3168€

Kit Silicone vaginal dilator (ref 69-4805-05-3) 44 units x 34,95 € (50% patients of the study) = 1537,8€

Vaginal vibrator (ref. 729232) x 88 units x € 8.95 =787,6€

Vaginal lubricant tube 100 mL x 616 IU x € 3,5 (for 88 patients throughout the study) = 2156€

Moisturizer hyaluronic acid-based ovules (Cerviron®) provided free of charge by Interpharm (for 88 patients throughout the study) = 0€

CO2 laser equipment: The SMARTXIDE TOUCH provided free of charge by DEKA = 0€

Tablet:

Smartphone and phone line (18 months - study phone contact):

C) Travel Expenses

Dissemination of the results of the study of national / international conferences 1500€

COST CATEGORY	COST
1. Personnel	20.830,6 €
2. Consumables and services	7669,4 €
3. Travel expenses	1.500 €
TOTAL	30.000

SCHEDULE:

	0-1	2-3	4	5	6	7	8	9	10	11-14	15	16	17	18
Database design	■													
Recruitment	■	■												
Baseline visit		■	■											
Treatment			■	■	■	■	■	■						
Follow-up visits								■	■		■	■		
Cytology		■	■					■	■		■	■		
Questionnaires		■	■					■	■		■	■		
Analysis results												■	■	
Manuscript edition													■	■

ATTACHMENTS:

Please attach:

CV of the PI including list of all peer reviewed publications

Copies of ethics and regulatory permissions

Any figures or tables

Table 1: inclusion and exclusion criteria

Inclusion Criteria	
	BC treated with aromatase inhibitors ± GnRH analogues (aGnRH)
	Menopause (natural or induced) and signs / symptoms of GSM; Vaginal pH ≥ 5
	Negative Human Papillomavirus (HPV) cytology and / or determination
	Intention or willingness to have sex
	Signed informed consent
Exclusion criteria	
	Vaginal hormonal treatment in the last 6 months
	Vaginal moisturizers and / or lubricants during the 30 days prior to study treatment
	Laser treatment, radiofrequency, hyaluronic acid, lipofilling in the vagina during the last 2 years
	Ospemifene treatment
	Being affected for: active infection of the genital tract; intraepithelial neoplasm of cervix, vagina, or vulva; have or have been treated for genital cancer; Genital prolapse stage \geq II.

ANNEXED:

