Annex 1: STUDY STRUCTURE (Table 2):

A) Screening/Recruitment telematic visit (T-2): to select eligible patients and to deliver information sheet and explanation of the project.

B) Screening/Recruitment presential visit (T-1): to perform physical examination and sexual assessment, to confirm eligibility and to sign informed consent.

C) Baseline presential Visit (T0): to fill in baseline questionnaires and to assess sexuality using PLISSIT Model according usual care in our hospital.

D) Treatment visits: T1 (session 1), T2 (session 2), T3 (session 3), T4 (session 4), T5 (session 5): to perform the intervention according previous description.

E) Follow-up visits: T6 (1 month after session 5), T12 (7 months after session 5): to perform physical examination and fill in questionnaires at short and mid-term. Out of timeline project, a visit T24 (13 months after session 5) is planned as usual care practice in our hospital to assess outcomes at long-term follow-up (also approved by our Ethical Committee).

Table 2. Study structure

Endpoint	Instrument	T-2	T-1	T0	T1-T5	T6	T12
Inclusion/exclusion criteria	Checklist database	X					
Trial information	Delivery Written and verbal information Signature Informed consent	X	X				
Baseline characteristics	General Anamnesis BC Anamnesis Sexual Anamnesis Socio-demographic data	X X X X		X			
Physical examination	Gynaecological examination VHI of Gloria Bachmann * ¹ Vaginal pH * ² Maturation index * ³ (vaginal cytology) Liquid cytology (reflex HPV determination) Pelvic floor muscle function		X X X X X			X X X X X	X X X X
GSM symptoms	VAS dispareunia * ⁴ VAS dryness * ⁴ VAS burning * ⁴ ICIQ-IU-SF + CACV			X X X X		X X X X	X X X X
Sexual symptoms	FSFI total score * ⁵ VAS sexual life distress * ⁴			X X		X X	X X
Body image	S-BIS * ⁶			X		X	X
Generic quality of life	SF-12 * ⁷			X		X	X
Intervention	Laser vs sham				X		
Adherence to treatment	Adherence diary				X		
Adverse events	Database/ AEs form				X	X	X
Treatment satisfaction	Likert scale					X	X

*¹Evaluation of the Vaginal Health Index of Gloria Bachmann: An exploration of the lower genital tract will be carried out and the degree of AVV will be assessed through

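### Read literally, the plan randomises women at the second visit (T-1), before the baseline FSFI is collected at T0, and no text makes allocation wait for the cytology/HPV result

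*Combined protocol and SAP*

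**What the plan says.** **Ethics section (ETHICAL AND REGULATORY PERMISSIONS).** Women first receive information at a telematic visit. "After an interval of at least 48h the patient will have a second visit (presential"), at which the signed consent is checked. The next sentence reads: "Both in- and exclusion criteria will be reviewed and if found suitable, the patient will be randomized". No visit code is given.

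**Annex 1.** T-2 is the telematic screening visit. T-1 is the in-person screening visit, whose purpose is "to perform physical examination and sexual assessment, to confirm eligibility and to sign informed consent". T0 is a separate, later visit: "Baseline presential Visit (T0): to fill in baseline questionnaires and to assess sexuality using PLISSIT Model". Treatment sessions are T1 to T5. Randomisation is not listed at any visit.

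**Table 2.** The FSFI, VAS items, S-BIS and SF-12 have their first mark at T0. There is no randomisation row. The eligibility row reads "Inclusion/exclusion criteria Checklist database X", a single mark that appears to sit under T-2. The physical-examination block includes "Liquid cytology (reflex HPV determination"), with its first marks under T-1.

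**Table 1.** One inclusion criterion is "Negative Human Papillomavirus (HPV) cytology and / or determination".

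**STATISTIC ANALYSIS.** The comparison is of change from baseline, in an MMRM adjusted for the baseline value. The main analysis is by ITT.

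**The concern.** A baseline covariate should be measured before allocation, so that it cannot depend on the assigned arm and so that every randomised woman has one. Here the only text that gives randomisation a place in the sequence puts it one visit too early for that. Three things are at stake.

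1. **Missing baselines in the ITT set.** A woman randomised at T-1 who does not return for T0 counts under ITT but has neither a covariate nor a change score. The plan has no rule for her. This problem does not depend on any failure of blinding.
2. **Influence on the baseline.** The FSFI is self-reported, and PLISSIT counselling also takes place at T0. If allocation were known or guessed by then, both could be affected, and adjusting for baseline would carry the effect into the treatment estimate.
3. **Entry criteria not yet settled.** If the cytology/HPV result is still pending when a woman is randomised, she may later prove not to meet Table 1, and the trial must then decide how ITT treats her.

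**Working it through.** **Step 1: match the visits.** The ethics section and Annex 1 describe the same sequence.

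| Feature | Second visit, ethics section | T-1, Annex 1 | T0, Annex 1 |
|---|---|---|---|
| Order | second contact | second contact | third contact |
| Mode | in person | in person | in person |
| Consent | checked | signed | not listed |
| Eligibility | reviewed | confirmed | not listed |
| Randomisation | follows the review | not listed | not listed |
| Baseline FSFI | not mentioned | not marked | first marked |

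The second visit matches T-1 in order, mode and content, and does not match T0. Nothing elsewhere overrides the resulting order: randomise, then collect the baseline FSFI.

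**Step 2: cytology/HPV.** A negative result is required by Table 1. The sample appears to be taken at T-1, but Table 2 is flattened: six examination instruments share five marks under T-1, so the mark for this row is likely and not certain. The documents give no turnaround time, do not say whether an earlier result is accepted, and do not say that allocation waits. Separately, the exclusion for recent moisturisers or lubricants counts back 30 days from study treatment, so its window may also still be open at T-1.

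**Step 3: illustration of lost women.** The plan gives 44 per arm, two-sided alpha 0.05, beta below 0.1, SD 1 and 15% loss. It states no detectable difference, so 44 can only be back-solved:

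- difference = sqrt(2/n) × (1.960 + 1.282)
- n = 44: 0.691 SD
- n = 44 × 0.85 = 37.4: 0.750 SD

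Now assume that a further share p of randomised women is absent from the primary analysis, whether for want of a baseline or because they are removed as ineligible. No such rate is in the documents. With power = Φ(0.75 × sqrt(n/2) − 1.960) and n = 37.4 × (1 − p):

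| p (assumed) | Women of 88 | n per arm | Power at 0.75 SD |
|---|---|---|---|
| 0 | 0 | 37.4 | 90.0% |
| 5% | 4.4 | 35.5 | 88.5% |
| 10% | 8.8 | 33.7 | 86.8% |
| 15% | 13.2 | 31.8 | 84.9% |

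**Step 4: illustration of baseline influence.** In a baseline-adjusted model, a spurious arm difference in baseline moves the estimated effect by slope × difference, in the opposite direction. With an assumed slope of 0.5 to 0.7 and an assumed 1-point difference, the shift is 0.5 to 0.7 FSFI points. If allocation stays concealed, the expected difference is zero and so is the bias.

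**The case against.** **The text sets a condition, not a date.** The ethics section uses no visit code, and its sentence could mean randomisation at some later point once every criterion is known. Annex 1 is the actual schedule and does not list randomisation at T-1. This stands in part: placement at T-1 is a literal reading and not an explicit statement. But no text supplies the later point, and by sequence the plain reading is T-1.

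**A reader might infer that the plan lets ineligible women be randomised.** The documents do not support that. Suitability on all criteria is made a precondition, so a pending HPV result means that the criterion is not yet met. Nor do they show that the result is unavailable at T-1, since an earlier or same-day result is not ruled out. What remains is that no text says allocation waits for the result.

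**A reader might infer that the primary comparison is biased.** That is not supported either. The trial is described as double-blind and sham-controlled, no laser or sham session precedes T1, and PLISSIT is usual care in both arms. Bias at T0 needs allocation to be known or guessed. Blocks of 2 make guessing easier once one assignment in a pair is revealed, but that is a separate weakness which moving randomisation would not cure.

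**Mistaken randomisations are to be replaced.** They are, and the technical error given is only an example. The rule does not say whether a replaced woman stays in the ITT set, and it does not cover a missing baseline.

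**Conclusion.** The point holds as a sequencing gap with a real consequence for the primary analysis. Followed literally, the plan allocates women before their primary-outcome baseline is taken. Exposure to missing baselines in the ITT set follows from that order alone. Influence on the baseline is conditional on allocation becoming known or guessed. The cytology/HPV element is a risk arising from an unstated result time.

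The conclusion rests on identifying the second in-person visit of the ethics section with T-1, which order, mode and content support. Its size cannot be taken from the documents. The fall in power to between 88.5% and 84.9% and the shift of 0.5 to 0.7 points are illustrations under assumed rates, an assumed slope and a back-solved difference of 0.75 SD. Neither is a prediction.

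**What to change.** Reconcile the ethics section with Annex 1:

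- State that randomisation takes place only after the T0 questionnaires are completed and all eligibility results, including cytology/HPV, are on file, and before session 1 (T1).
- Add a randomisation row to Table 2, placed between T0 and T1.

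A woman who does not attend T0 is then never randomised, and every woman in the ITT set has had the chance to give a pre-allocation baseline.

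The cost is a sentence of protocol text and one table row. No extra visit or patient is needed. The small downside is that allocation occurs slightly later.

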Annex 1: STUDY STRUCTURE (Table 2):

A) Screening/Recruitment telematic visit (T-2): to select eligible patients and to deliver information sheet and explanation of the project.

B) Screening/Recruitment presential visit (T-1): to perform physical examination and sexual assessment, to confirm eligibility and to sign informed consent.

C) Baseline presential Visit (T0): to fill in baseline questionnaires and to assess sexuality using PLISSIT Model according usual care in our hospital.

D) Treatment visits: T1 (session 1), T2 (session 2), T3 (session 3), T4 (session 4), T5 (session 5): to perform the intervention according previous description.

E) Follow-up visits: T6 (1 month after session 5), T12 (7 months after session 5): to perform physical examination and fill in questionnaires at short and mid-term. Out of timeline project, a visit T24 (13 months after session 5) is planned as usual care practice in our hospital to assess outcomes at long-term follow-up (also approved by our Ethical Committee).

Table 2. Study structure

Endpoint	Instrument	T-2	T-1	T0	T1-T5	T6	T12
Inclusion/exclusion criteria	Checklist database	X					
Trial information	Delivery Written and verbal information Signature Informed consent	X	X				
Baseline characteristics	General Anamnesis BC Anamnesis Sexual Anamnesis Socio-demographic data	X X X X		X			
Physical examination	Gynaecological examination VHI of Gloria Bachmann * ¹ Vaginal pH * ² Maturation index * ³ (vaginal cytology) Liquid cytology (reflex HPV determination) Pelvic floor muscle function		X X X X X			X X X X X	X X X X
GSM symptoms	VAS dispareunia * ⁴ VAS dryness * ⁴ VAS burning * ⁴ ICIQ-IU-SF + CACV			X X X X		X X X X	X X X X
Sexual symptoms	FSFI total score * ⁵ VAS sexual life distress * ⁴			X X		X X	X X
Body image	S-BIS * ⁶			X		X	X
Generic quality of life	SF-12 * ⁷			X		X	X
Intervention	Laser vs sham				X		
Adherence to treatment	Adherence diary				X		
Adverse events	Database/ AEs form				X	X	X
Treatment satisfaction	Likert scale					X	X

*¹Evaluation of the Vaginal Health Index of Gloria Bachmann: An exploration of the lower genital tract will be carried out and the degree of AVV will be assessed through

([https://www.maturitas.org/article/0378-5122\(95\)00956-6/pdf](https://www.maturitas.org/article/0378-5122(95)00956-6/pdf)). This index subjectively assesses the vagina's staticity, the amount of discharge, the integrity of the epithelium and humidity, along with pH as the only objective criterion. A score of ≤ 15 indicates AVV. It is the Index most used in publications reporting improvement of AVV with the use of lasers.

*²Vaginal vaginal pH: Using a pH test strip, colorimetric analysis of the pH of the vaginal discharge is performed.

*³Maturative Index: Using vaginal cytology, the percentage of parabasal, intermediate and superficial cells is calculated, allowing us to calculate the epithelial thickness indirectly.

*⁴ Visual Analog Scale (VAS): Evaluates 3 symptoms of AVV: dyspareunia, dryness and burning. Score from 0 to 10 (unbearable symptom). Symptoms are considered moderate from ≥ 4 .

*⁵ Female Sexual Function Index (FSFI): Generic sexual questionnaire validated for cancer survivors. We used the 19-item self-reported Spanish validated questionnaire to assess 6 sexual dimensions (desire, arousal, lubrication, orgasm, satisfaction and pain) and the global sexual function. Score ranges from 1,6 to 36, with the higher score indicating a better sexual Function. Function. A cut-off value of ≤ 26.55 indicates risk of sexual dysfunction, however, it could inflate female sexual dysfunction rates in those women whose sexual activity frequency is lower than once a month or in non-sexually active women. (<https://scielo.conicyt.cl/pdf/rchog/v69n2/art06.pdf>)

*⁶ Body Image Scale-Spanish version (S-BIS): Assesses 10 domains of body image in 10 questions and is applicable in patients with any type of cancer and different therapeutic regimens. The total score ranges from 0 to 30. The higher the score, the greater the concern regarding body image. (<https://www.ncbi.nlm.nih.gov/pubmed/25135839>).

[figure not shown]
*⁷ Quality of life Short Form 12 (SF-12): It consists of 12 items from the 8 dimensions of the SF-36 Physical Function (2), Social Function (1), Physical Role (2), Emotional Role (2), Mental health (2), Vitality (1), Body pain (1), General Health (1). (http://www.ser.es/wp-content/uploads/2015/03/SF12_CUESTIONARIO.pdf)

VVA: Severity classification / assessment Vaginal Health Index (Gloria Bachmann)

Score	1	2	3	4	5
Elasticity	none	poor	fair	good	excellent
Fluid Volume (Pooling of Secretion)	none	Scant amount, vault not entirely covered	superficial amount, vault entirely covered	moderate amount of dryness (small areas of dryness on cotton tip applicator)	normal amount (fully saturates on cotton tip applicator)
pH	≥ 6.1	5.6 - 6.0	5.1 - 5.5	4.7 - 5.0	≤ 4.6
Epithelial Integrity	petechiae noted before contact	bleeds with light contact	bleeds with scraping	not friable – thin epithelium	normal
Moisture (Coating)	none, surface inflamed	none, surface not inflamed	minimal	moderate	normal

Table 1: Gloria Bachman Vaginal Health Index (VHI).

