STUDY GROUPS: All patients will receive instructions to maintain first-line non-hormonal treatment, as well as sexual assessment using the PLISSIT Model according with usual care in our hospital.

The study group will be treated with a vaginal fractionated CO2 laser protocol (The SMARTXIDE TOUCH (Deka) equipment with an autoclavable vaginal probe following the manufacturer's protocol (Annex 9).

The control group will receive treatment with a sham-CO2 laser using a double-blinded protocol.

STUDY STRUCTURE (See Annex 1).

SAMPLE CALCULATION

Considering FSFI score as the main variable of the study, we performed a calculation of the hypothesis contrast study sample with the comparison of two independent means. Accepting an alpha risk of 0.05 and a beta risk of less than 0.1 in a bilateral contrast, 44 subjects in the first group and 44 in the second. The common standard deviation is assumed to be 1. A follow-up loss rate of 15% has been estimated.

STATISTIC ANALYSIS

Descriptive statistics will be used according to standard calculation methods.

The comparison between the two treatments at the end of the study will be evaluated through the change with the baseline using a mixed repeated measures model (MMRM) adjusted for the baseline value and including the treatment and the time in the model.

The variables of repetitive evaluation over time are analyzed according to the following strategy: (a) continuous variables with a repeated measures mixed longitudinal model (MMRM); (b) binary or non-normal variables with marginal models (Generalized Estimating Equation: GEE). Other variables will be studied as follows: Fisher's exact test for categorical variables, Student's t test for continuous variables between 2 groups. Non-parametric methods for independent data (Mann-Whitney U for 2 groups or Kruskal-Wallis test for more than 2 groups) will be used if necessary. The level of statistical significance will be 5% bilateral. The main analysis will be by Intention to Treat (ITT).

REFERENCES:

1. World Health Organization. Defining sexual health. Report of a technical consultation on sexual health 28-31, January 2002, Geneva. Geneva: World Health Organization, 2006.
2. MI Maiorino, P Chiodini, G Bellastella, D Giugliano, K Exposito. Sexual dysfunction in women with cancer: a systematic review with meta-analysis of studies using the Female Sexual Function Index. *Endocrine* (2016) 54:329–3413.

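### With FSFI scheduled only at T0, T6 and T12, a woman lost before T6 adds nothing to the primary MMRM, so the ITT label covers only randomised women with a post-baseline FSFI

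*Combined protocol and SAP*

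**What the plan says.** Annex 1 describes the treatment visits as follows: "Treatment visits: T1 (session 1), T2 (session 2), T3 (session 3), T4 (session 4), T5 (session 5): to perform the intervention according previous description". Questionnaires come afterwards: "Follow-up visits: T6 (1 month after session 5), T12 (7 months after session 5): to perform physical examination and fill in questionnaires". Table 2 agrees. The sexual-symptom row ("FSFI total score * ⁵ VAS sexual life distress") is marked at T0, T6 and T12, while the T1-T5 column carries only the intervention, the adherence diary and adverse events. No assessment on leaving is listed.

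Aims names the FSFI total score as the primary outcome. Statistic Analysis compares the arms at the end of the study by an MMRM on change from baseline, adjusted for the baseline value, with treatment and time in the model. It labels the main analysis intention-to-treat. It does not define that set, gives no rule for women without a post-baseline FSFI, and plans no sensitivity analysis. Sample Calculation adds: "A follow-up loss rate of 15% has been estimated".

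Ethical and Regulatory Permissions lets women leave at any time. It also contains two sentences on withdrawal: "The investigator can decide to withdraw a subject from the study for urgent medical reasons" and "Patients withdrawn from the intervention but not from informed consent will be followed up".

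**The concern.** Sessions are 30 days apart and T6 is one month after session 5, so about five months of attended visits pass without a measurement of the primary outcome. A woman who leaves the study in that period has no change score. The model has no response from her to use and no on-treatment value from which to predict one.

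Leaving could plausibly depend on lack of improvement or on poor tolerance, and not equally in the two arms. If so, the women who remain are not comparable between arms, and the primary difference shifts although it is reported as ITT. Outcomes that were never measured cannot be recovered at the analysis stage.

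The two withdrawal sentences add a smaller uncertainty. One speaks of leaving the study, the other promises follow-up to women who leave the intervention. It is unclear which governs a woman stopped on medical grounds who keeps her consent.

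**Working it through.** **1. The planned loss.** Sample Calculation gives 44 per arm, two-sided alpha 0.05, beta below 0.1, SD 1 and 15% loss, but no detectable difference, so 44 cannot be reproduced from the stated inputs. Solving backwards with n = 2(1.960 + 1.282)²/δ²: at δ = 0.75, n = 21.015/0.5625 = 37.36, and 37.36/0.85 = 43.95, or 44. On that reading the 15% is already paid for in precision: power is 94.0% at 44 per arm and 90.0% at 37.4. Inflating the sample does nothing about bias.

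**2. Who is excluded.** 0.15 × 88 = 13.2, so about 13 women are expected to be lost. Only those lost before T6 fall out of the model. The documents do not give timing, so the number lies between 0 and about 13.

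**3. Size of bias by hand.** If a fraction f of one arm leaves and the leavers are k SD worse than those who stay, that arm's observed mean is too high by f × k. With f = 0.15 and k from 0.25 to 1, the shift is 0.15 × 0.25 = 0.04 to 0.15 × 1 = 0.15 SD. If f and k are the same in both arms, the shifts cancel.

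**4. Simulation.** Assumptions, none of them in the documents: 1,000,000 women per arm; unit SD; true difference 0.40 SD in mid-treatment and 0.50 SD at T12; correlations 0.6 (T0 with mid), 0.5 (T0 with T12) and 0.7 (mid with T12). Leaving is logistic in the mid-treatment change, with log-odds 1 or 2 per SD of worse change, and the loss is set to the same percentage in each arm. Planned analysis: T12 on T0 and arm among the women who stay.

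| Whose leaving depends on response | 15%, all before T6 | 7.5% before T6 |
|---|---|---|
| Both arms equally | 0.50 | 0.50 |
| Sham only | 0.45 / 0.41 | 0.47 / 0.45 |
| Laser only | 0.55 / 0.59 | 0.53 / 0.55 |

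Each pair is for log-odds 1 / 2. The largest biases are -0.09/0.50 = -18% and +0.09/0.50 = +18%. The 7.5% column treats later loss as adding no bias. If one common leaving rule applies to both arms, sham women leave more often because they respond less, and the estimate is 0.48 / 0.46.

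**5. Unequal loss.** A second simulation used 44 per arm, 4,000 runs, true difference zero, correlation 0.5, and leaving weighted by a poor T6 score. Loss of 15% in each arm gave bias 0.00 SD. Loss of 25% laser and 5% sham gave +0.15 SD and a type I error of 13.1%.

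**6. What one mid-treatment FSFI recovers.** The likelihood estimate is the arm effect on T12 given T0 and T3, plus the T3 slope times the baseline-adjusted arm difference at T3. In the setting of step 4 (15% loss, log-odds 2, one arm only):

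| Situation | Planned visits (sham only / laser only) | With T3 |
|---|---|---|
| Leaving follows the T3 score, every leaver has T3 | 0.41 / 0.59 | 0.50 / 0.50 |
| Same, 40% of leavers gone before T3 | 0.41 / 0.59 | 0.47 / 0.53 |
| Leaving follows the eventual T12 change, every leaver has T3 | 0.34 / 0.66 | 0.39 / 0.61 |

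The first row is perfect by construction, because the score that drives leaving is the one added to the model. In the third row about a third of the bias goes: 0.05/0.16.

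**The case against.** A reader might infer that this is a completer analysis. It is not. The follow-up sentence ("Patients withdrawn from the intervention but not from informed consent will be followed up") means that women who stop sessions are still due T6 and T12, and a woman with T6 but no T12 stays in the MMRM.

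A reader might also infer that the primary result is biased. The documents do not support that. They give no timing, cause or arm split for the 15%, the sign can go either way, and equally selective loss of equal size gave no bias. The plan also works against dropout: it offers every woman a further laser session at the end and the placebo group all five. That bears directly on selective loss from sham, although it cannot exclude it.

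Nor do the withdrawal sentences show that medically withdrawn women lose their T6 and T12 data. Someone withdrawn by the investigator has not withdrawn consent, and the follow-up sentence can be read to cover her. The wording is ambiguous, no more.

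Finally, an extra FSFI could be oversold. It does not cure informative loss (step 6). At 44 per arm and log-odds 2, root mean squared error falls only from 0.231 to 0.201 (sham only) and from 0.225 to 0.202 (laser only).

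All of this stands and limits the claim. What remains is that women lost before T6 are left out of an analysis called ITT and that nothing in the plan deals with them. In every biased scenario examined, the added measurement moved the estimate towards the truth.

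**Conclusion.** The concern holds in limited form. The primary analysis set is randomised women with at least one post-baseline FSFI, and the plan neither says so nor handles the women outside it. The possible bias runs in either direction. Under the step 4 assumptions with one-arm selection it is up to about 0.09 SD (15% loss, all before T6) or 0.05 SD (half of it before T6), and zero when equally selective loss is balanced. These figures illustrate and do not bound the bias: selection on the eventual outcome gave 0.34 to 0.66 SD. All rest on an assumed true difference of 0.50 SD, which the documents do not state. This is a worthwhile, inexpensive improvement, not a flaw that invalidates the trial.

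**What to change.** 1. Add the self-completed FSFI at one existing treatment visit, for example T3 before the session, as a post-baseline time point in the MMRM. Keep the end-of-study contrast as the target. This needs a treatment-by-visit term, so that the T3 difference is not averaged into that contrast; the plan names only treatment and time. The form's four-week recall fits the 30-day spacing.
2. Ask any woman leaving before T6 who agrees for one FSFI by phone or tablet. For women leaving before T3 this is the only post-baseline value. The budget already lists a tablet and a study phone line.
3. Define the ITT set, state the rule for women without a post-baseline FSFI, and add a delta-adjusted or reference-based sensitivity analysis that includes all randomised women. Report loss by arm and by timing (before or after T6).
4. Reconcile the two withdrawal sentences in Ethical and Regulatory Permissions, so that it is clear whether T6 and T12 data are still collected from women who keep their consent. The medical grounds for stopping need no change.

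Cost: one more 19-item form, a few minutes per woman at a visit she already attends; occasional exit calls; one more time point in the model; and some drafting. The result is less bias, not none.
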